7.4.2.1. Hematology

1. Erythrocytes: red blood cell count, hematocrit, hemoglobin, mean corpuscular volume
2. Leukocytes: white blood cell count and differential (basophils, eosinophils, lymphocytes, monocytes, and neutrophils)
3. Platelets: platelet count

7.4.2.2. Coagulation Panel

1. PT with INR and PTT

7.4.2.3. Serum Chemistry

1. Liver: Alkaline phosphatase, ALT (serum glutamic-pyruvic transaminase), AST (serum glutamic-oxaloacetic transaminase), bilirubin (total, direct), gamma-glutamyl transferase, and lactic dehydrogenase
2. Renal: blood urea nitrogen and creatinine
3. Electrolytes: sodium, potassium, chloride, carbon dioxide, calcium, magnesium, phosphate
4. General: total protein, albumin, glucose
5. Lipids: cholesterol (total) and triglycerides

7.4.2.4. Urinalysis

1. pH
2. Protein
3. Glucose
4. Ketones
5. Blood
6. Bilirubin

7.4.3. Urine or Serum Pregnancy Test

Both men and women should be counseled to abstain from sexual activity or use an acceptable method of birth control (Section 7.5.10) while participating in this clinical research study and for 30 days afterwards. They are required to use acceptable methods of birth control. Female subjects who become pregnant should be immediately discontinued from the study if they have not yet received study drug. If a subject is found to be pregnant after she has received study drug, she should discontinue dosing, complete all end of study procedures, and be followed to determine the outcome of the pregnancy. Generally, follow-up will be no longer than 6 to 8 weeks following the estimated delivery date. See Section 7.5.11 for rules regarding reporting pregnancies.

Human chorionic gonadotropin beta subunit will be measured on all female subjects of childbearing potential at Screening, Baseline, Weeks 4, 8, and 12 and every 12 weeks thereafter throughout the study. If a subject cannot perform a urine pregnancy test at any timepoint, a serum pregnancy test should be performed. At-home urine pregnancy test kits will be provided; subjects will be required to perform the test at home 30 days after the last dose of study drug and self-report the results via telephone.

7.4.4. Laboratory Abnormalities

Laboratory values will be collected throughout the study to assess for safety. The investigator must review and assess all laboratory results in a timely manner, and determine whether the abnormal laboratory values, if any, are clinically significant or not clinically significant, and whether there are associated signs and symptoms. The investigator must make the determination whether the clinically significant abnormal laboratory values are AEs.

An abnormal laboratory finding in absence of any other signs or symptoms is not necessarily an AE. If the abnormal laboratory finding is accompanied by signs or symptoms, report the signs and symptoms as the AE in lieu of the abnormal laboratory value. If a diagnosis is available, report the diagnosis. Clinically significant laboratory abnormalities after taking study medication that reflect a meaningful change from the screening value(s) and that require active management are to be considered by the investigator as AEs (eg, abnormalities that require study treatment dose modification, discontinuation, more frequent follow-up assessments, etc).

7.4.4.1. Grade 3 or 4 Laboratory Abnormalities

Diagnoses associated with any CTCAE Version 5.0 Grade 3 or 4 laboratory abnormalities will be recorded as AEs on the eCRF. Repeated and verified laboratory tests that meet at least

Grade 3 AE requirements will be reported to the Institutional Review Board/Institutional Ethics Committee (IRB/IEC) per institutional requirements. The recorded AEs should indicate the underlying abnormality or diagnosis (eg, renal insufficiency) if known, as opposed to the observed deviation in laboratory results (eg, elevated creatinine). Any additional relevant laboratory results obtained by the investigator during the study will be supplied to the sponsor.

7.4.5. Dose-Limiting Toxicity

No dose-limiting toxicities or other drug-related laboratory abnormalities were reported in prior clinical studies. In preclinical studies, prolongation of PT was identified as the NOAEL. Coagulation parameters (PT [can be measured as INR] and PTT) will be monitored throughout this study.

7.4.6. Dose Modification Guidelines and Stopping Rules

In the event that any subject develops any AE \geq Grade 3 per CTCAE criteria version 5.0 in severity that is deemed related to treatment with study drug and not related to the underlying disease, the Principal Investigator should contact PTC's medical monitor to discuss dose modification options up to and including discontinuation of the administration of study drug.

In the event that any subject develops or is diagnosed with an allergy to vatiquinone or sesame oil after initiating treatment with study drug, administration of study drug will be discontinued.

In the event that any subject develops elevated INR \geq Grade 2 in severity ($>1.5 \times \text{ULN}$) per CTCAE criteria version 5.0 thought to be related to treatment with study drug, administration of study drug will be reduced to 66%. Should the INR toxicity not resolve to at least Grade 1 in severity within 2 weeks of the initial dose reduction, administration of study drug may either be further reduced or discontinued (Table 3).

Once a subject's dose is reduced due to elevated INR thought to be related to study drug administration, their dose should not be re-escalated.

Table 3: Dose Modification and Stopping Rules for Vatiquinone

Qualifying Event	Example Guidelines for Management		
	Recommendation	If Resolved to \leq Grade 1	If Not Resolved to \leq Grade 2 After 14 Days
INR \geq Grade 2 or $>1.5 \times \text{ULN}$ thought to be related to study drug and confirmed within 24-48 hours	Reduce dose by 1/3 from TID to BID Re-evaluate 7 days after dose reduction	Continue on-study at 2/3 dose.* *Once a subject is dose reduced, do not re-escalate.	Consider withdrawing the subject after consultation with the study medical monitor.

Abbreviations: AE, adverse event; DSMB, Data Safety Monitoring Board; INR, International Normalized Ratio; ULN, upper limit of normal

The investigator is responsible for decisions on dose holds, reductions, or interruptions for any clinically significant AE. The DSMB is responsible for determining dose modification or stopping actions for any other safety event.

7.4.7. Safety Guidance

PTC may request that the investigator perform or arrange for the conduct of supplemental measurements and/or evaluations. If a subject dies during participation in the study or during a recognized follow-up period, PTC should be provided with a copy of any post-mortem findings, including histopathology.

7.5. Adverse Events and Serious Adverse Events

7.5.1. Definition of Adverse Events

An AE is any untoward medical occurrence associated with the use of a drug in humans, whether or not it is considered related to the drug. An AE can therefore be any unfavorable and unintended sign (including an abnormal laboratory finding), symptom, or disease in a study subject who is administered study drug in this study.

For this protocol, untoward medical occurrences that should be reported as AEs include the following:

- All AEs during the course of treatment with study drug administration
- All AEs resulting from medication misuse, abuse, withdrawal, or overdose, of study drug
- All AEs resulting from medication errors such as dispensing or administration error outside of what is described in the protocol
- Apparently unrelated illnesses, including worsening of a preexisting illness
- Injury or accidents. Note that if a medical condition is known to have caused the injury or accident (a fall secondary to dizziness), the medical condition (dizziness) and the accident (fall) should be reported as 2 separate AEs. The outcome of the accident (hip fracture secondary to the fall) should be recorded in source documents.
- Abnormalities in physiological testing or physical examination findings that require clinical intervention or further investigation (beyond ordering a repeat [confirmatory] test)
- Laboratory or ECG abnormalities that require clinical intervention or further investigation (beyond ordering a repeat [confirmatory] test) unless they are associated with an already reported clinical event. Laboratory abnormalities associated with a clinical event should be captured in the source documents. Laboratory abnormalities not requiring clinical intervention or further investigation will be captured as part of overall laboratory monitoring, and should not be reported as AEs.
- A preexisting condition (eg, allergic rhinitis) must be noted on the appropriate eCRF, but should not be reported as an AE unless the condition worsens or episodes increase in frequency during the AE reporting period. Diagnostic and therapeutic noninvasive and invasive procedures, such as surgery, should not be reported as AEs. However, the medical condition for which the procedure was performed should be reported if it meets the definition of an AE. For example, an acute appendicitis that occurs during the treatment with study drug should be reported as the AE and the resulting appendectomy should be recorded in the source documents and eCRF. If a surgical procedure was planned prior to entry into the study, and the surgery is not performed because of a worsening of a baseline condition, this should not be reported as an AE. Note that, as described in Section 7.5.2 any hospitalization occurring as the consequence of an AE during the study period should be reported as an SAE.

Each AE is to be classified as serious or nonserious by the investigator using medical and scientific judgment.

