1.5. Risk/Benefit Assessment

1.5.1. Risk Assessment

At the dose levels selected for this study it is not foreseen that subjects will endure any risks greater than minimal. However, as the dose-limiting adverse effect in nonclinical toxicology studies was anticoagulation, to further minimize potential risks subjects will be frequently monitored for changes in coagulation parameters and other clinical pathology assessments. Administration of study drug will be adjusted or completely stopped if coagulation parameters (PT, partial thromboplastin time [PTT]) are found to be increased to more than 1.5×upper limit of normal (ULN).

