7.5.5. Recording Nonserious AEs and SAEs

All AEs (both serious and nonserious) that occur in subjects during the AE reporting period must be recorded, whether or not the event is considered drug-related. In addition, any known untoward event that occurs subsequent to the AE reporting period that the investigator assesses as possibly related to the investigational drug/product should also be recorded as an AE.

All AEs are to be recorded in the source documents and on the eCRF using concise medical terminology; whenever possible, terms contained in the Medical Dictionary for Regulatory Activities should be employed. In addition, the following information should be recorded:

- Indication of whether the event is serious or nonserious (see Section 7.5.2)
- Relationship to study drug (see Section 7.5.6)
- Severity of the event (see Section 7.5.7)
- Onset date
- Resolution date, or date of death
- Action taken
- Outcome of the event

Classification of the event as serious or nonserious determines the reporting procedures to be followed.

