6.2. Adverse Events

The AE verbatim descriptions (investigator terms from the CRF) will be classified into medical terminology using the MedDRA. AEs will be coded by System Organ Class (SOC) and PT using MedDRA, Version 23.0 or later.

AE summaries will be presented by treatment for double-blind period, and by treatment sequence and overall for on-vatiquinone period, unless specified otherwise.

Only treatment-emergent AEs (TEAEs) will be included in summary tables. All AEs will be presented in subject data listings.

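### Protocol 7.5.1 sends the injury from a medically caused accident to source documents without naming the eCRF, so the injury term may be missing from the coded AE tables

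*Protocol*

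**What the plan says.** Protocol 7.5.1 lists what is to be reported as an AE. One item opens: "Injury or accidents. Note that if a medical condition is known to have caused the injury or accident (a fall secondary to dizziness" (the example then closes). In that situation "the medical condition (dizziness) and the accident (fall) should be reported as 2 separate AEs". The note ends with the injury itself: "The outcome of the accident (hip fracture secondary to the fall) should be recorded in source documents".

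Later in the same section, on procedures that follow an AE, the destination is wider: "the resulting appendectomy should be recorded in the source documents and eCRF".

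Protocol 7.5.5 gives the general rule. "All AEs (both serious and nonserious) that occur in subjects during the AE reporting period must be recorded", and on where they go, "All AEs are to be recorded in the source documents and on the eCRF using concise medical terminology". It also asks for seriousness, relationship and severity for each event.

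SAP 6.2 states what feeds the safety tables: "The AE verbatim descriptions (investigator terms from the CRF) will be classified into medical terminology using the MedDRA". SAP 6.2.1 then tabulates those coded terms by system organ class and preferred term, by maximum CTCAE grade and by relationship to study drug.

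**The concern.** A fracture or haematoma after a fall is an untoward medical occurrence and meets the AE definition at the head of 7.5.1. The note nevertheless stops at two AEs and gives the injury a different destination. A site that follows it literally enters the condition and the fall, and keeps the fracture in the chart. Another site, relying on 7.5.5, enters all three. The coded data would then depend on which sentence the site read.

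Two features of this trial make the gap worth closing. Entry requires at least 6 observed motor seizures in the 28 days before baseline, so a seizure followed by a fall and an injury is foreseeable and fits the note's condition of a known medical cause. Protocol 1.5.1 also explains the coagulation monitoring on the ground that anticoagulation limited dosing in animals: "as the dose-limiting adverse effect in nonclinical toxicology studies was anticoagulation". Bleeding after trauma is one way such an effect could show itself. At stake is whether an injury of that kind can be seen under its own name when the arms are compared.

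**Working it through.** No arithmetic applies: the plan gives no figure on this point and none can be derived. The check sets the relevant texts side by side.

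1. **Destination of the injury (7.5.1, accident note).** Source documents. Neither the eCRF nor the AE page is mentioned.
2. **How 7.5.1 uses the term elsewhere.** Laboratory abnormalities tied to a clinical event also go to source documents, and they are not reported as separate AEs. The appendectomy example names source documents and the eCRF together. Within one section, then, naming source documents alone goes with no separate AE entry, and the eCRF is named when it is wanted. A site could reasonably read the fracture sentence the same way.
3. **Conflict inside the bullet.** The item begins by listing injuries, as well as accidents, as occurrences to report. Its last sentence treats the injury as an outcome to be filed.
4. **Conflict with 7.5.5.** All AEs go in both places. The accident sentence neither cites this rule nor says that it is an exception to it.
5. **Path to the tables.** SAP 6.2 codes investigator terms from the CRF. A term that is only in the chart is not coded, so it cannot appear in the tables by preferred term, grade or relationship.
6. **What remains when the note is followed literally.** The condition and the fall are two coded AEs. Under 7.5.7 the highest grade attained in an episode is reported, so the severity of the injury may be reflected in the grade given to the fall. Under 7.5.1 and 7.5.2, hospitalization, death, threat to life and lasting disability make the event an SAE.
7. **What may be lost.** The injury's own term, and the separate grade, seriousness and relationship judgement that 7.5.5 attaches to each AE. The SAE route does not guarantee the term: 7.5.9 asks for the same AE term on the SAE form and the eCRF, which could be the fall. Short admissions for observation or minor treatment are outside the hospitalization criterion in 7.5.2, so some treated injuries would be nonserious.

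Steps 1 to 5 establish the inconsistency and the route by which a term can drop out. Steps 6 and 7 bound it: the specific injury may be lost, while the accident is kept.

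**The case against.** The strongest reply is that this is loose wording with several safeguards around it. The bullet itself makes injuries reportable. A neighbouring item in 7.5.1 covers examination findings that need intervention or further work-up, which would take in many fractures and haematomas. When 7.5.1 means to exclude something from AE reporting it says so outright, and the fracture sentence contains neither an exclusion nor the word only. Section 7.5.5 covers all AEs. Serious injuries reach the sponsor within 24 hours, and 7.4 has the DSMB notified of all AEs and SAEs. For anticoagulation, the planned detection route is the serial coagulation panel and the INR thresholds in SAP 6.3.

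Much of this stands, and it rules out several stronger readings that a reader might infer:

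- That fall injuries never reach the safety tables. The note covers only accidents with a known medical cause, the fall is tabulated, and serious cases are reported.
- That severity is necessarily understated, or that the contact rule for Grade 3 or higher events in 7.4.6 is missed. The highest grade of the episode is reported, and that rule applies only to events judged drug-related and not due to the underlying disease.
- That traumatic bleeding is singled out or exempted. The sentence does not mention bleeding; including it is an inference from the fracture example.
- That anticoagulation is a known clinical toxicity. It is a rat and dog finding (1.4.1). Protocol 7.4.5 reports no dose-limiting toxicity in prior clinical studies, and 1.4.2 reports no coagulation changes deemed associated with the drug.

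The reply does not remove the inconsistency. The general rule in 7.5.5 protects only what a site regards as an AE in its own right, and the more specific sentence points the other way. Laboratory monitoring does not record that a subject bled.

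**Conclusion.** The point holds as an internal inconsistency with a limited but real consequence. Followed literally, the accident note may keep the specific injury term, with its own grade and relatedness judgement, out of the system organ class and preferred term tables in SAP 6.2. The accident remains in those tables, and serious cases are still reported as SAEs.

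Its size cannot be stated. The documents give no rate of falls or injuries and do not show how sites read the sentence, so any percentage would be invented. The conclusion assumes that at least some sites follow the note as written, and that the eCRF completion instructions, which are not among these documents, do not already override it. The change is worth making because fall injuries are foreseeable in this population, the nonclinical finding gives traumatic bleeding some interest, and the correction is cheap.

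**What to change.** Replace the last sentence of the accident item in Protocol 7.5.1, or issue the same text in the eCRF completion guideline, along these lines: the resulting injury (for example a fracture, haematoma or laceration) is recorded as a separate AE on the eCRF, linked to the accident, with its own term, grade, seriousness and relationship to study drug. That brings the item into line with 7.5.5.

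Before the soft lock, and so before the sponsor is unblinded, query every reported fall or accident in both arms for an injury held only in source documents, and add the missing AE lines.

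The SAP needs no change, because its tables will pick up the added terms. No dose, stopping or other clinical rule is affected. The cost is one sentence, one extra AE line per injurious accident and a short query round for events already reported.

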7.5.2. Definition of Serious Adverse Events

An SAE is an untoward medical occurrence or effect associated with the use of a study drug at any dose, regardless of whether it is considered to be related to the study drug, which results in one of the following:

- Results in death. This includes all deaths on treatment or within 30 days after last study drug administration, including deaths due to disease progression. Any death occurring later than 30 days following the last dose need not be reported as an SAE unless it is a result of an event that started within the period covered by the on-study definition. The reported AE should be the event that caused the death. In addition, any AE resulting in death that occurs subsequent to the AE reporting period and that the investigator assesses as possibly related to the study drug should also be reported as serious.
- Is life-threatening. This refers to an event in which the subject was at risk of death at the time of the event. It does not include an event that, had it occurred in a more severe form, hypothetically might have caused death.
- Requires hospitalization or prolongation of existing hospitalization (excluding hospitalizations for administration of the study drug, procedures required by the study protocol, or treatment-related diagnostic procedures; other planned hospitalizations; or hospitalizations related only to progression of disease).

Medical and scientific judgment should be exercised in deciding whether expedited reporting is appropriate in other situations, such as important medical events that may not be immediately life-threatening or result in death or hospitalization but may jeopardize the subject or may require intervention to prevent one of the other outcomes listed in the definition above. These should also usually be considered serious. Examples of such events are intensive treatment in an emergency room or at home for allergic bronchospasm; blood dyscrasias or convulsions that do not result in hospitalization; or development of drug dependency or drug abuse.

Additionally, hospitalization should be used as an indicator of the seriousness of the AE and should only be used for situations where the AE truly fits this definition and not for hospitalizations associated with less serious events (eg, a hospital visit where a subject is admitted for observation or minor treatment [eg, hydration] and released in less than 24 hours). Furthermore, hospitalization for pharmacokinetic sampling, is not an AE, and therefore is not to be reported either as a routine AE or in an expedited report.

- Results in persistent or significant disability or incapacity or substantial disruption of the ability to conduct normal life functions.
- Any other medically important event that the investigator or the sponsor judges to be serious or which is defined as serious by the regulatory agency in the local country. These are AEs that might not be immediately life-threatening or result in death or

hospitalization but might jeopardize the subject or might require intervention to prevent one of the other outcomes listed above. Medical judgment should be exercised in deciding whether an AE is serious based on above definition. Examples of such events are intensive treatment in an emergency room or at home for allergic bronchospasm, blood dyscrasias or convulsions that do not result in hospitalization, or development of drug dependency or drug abuse.

- A pregnancy resulting in spontaneous abortion, stillbirth, neonatal death, or congenital anomaly (including that in an aborted fetus).

Serious adverse events will be assessed from the time of the Screening Visit through 30 days after the end of the subject's participation in the study (last dose) and should be reported to the sponsor if the investigator becomes aware of them.

